3.2.2 Secondary endpoints

3.2.2.1 Time to first COPD exacerbation

Time from randomisation to the first moderate or severe COPD exacerbation up to Week 52 will be a secondary efficacy variable, and is calculated as follows:

$$\text{Start date of first COPD exacerbation} - \text{Date of randomisation} + 1$$

An exacerbation event will be defined in the same way as outlined in Section 3.2.1.1. The time to first COPD exacerbation for subjects who complete Visit 16 (EOT) and do not experience a COPD exacerbation will be censored at Visit 16 date. For subjects who are lost to follow-up, prematurely withdraw from the study or discontinue the study treatment and remain in the study, the time to first COPD exacerbation will be censored at the end of the maximum follow-up time, as described in Section 3.2.1.1.

3.2.2.2 Proportion of subjects exacerbation free at Week 52

The proportion of subjects exacerbation free at Week 52 will be a secondary efficacy variable.

A moderate or severe exacerbation event will be defined in the same way as outlined in Section 3.2.1.1. In the statistical analysis, a binary variable taking on the value 1 if a subject has not experienced any moderate or severe exacerbations from randomisation to Visit 16 (EOT) and 0 otherwise, will be used as the response variable. The response variable will be set to 0 for subjects who withdraw early without completing Visit 16 (EOT).

3.2.2.3 Annual rate of severe COPD exacerbations

The annual rate of severe COPD exacerbations over 52 weeks will be a secondary efficacy variable. If the cause of any death is related to COPD or a COPD exacerbation, the event will also be included.

In the analysis, the number of severe COPD exacerbations will be used as response variable. The annual rate of severe COPD exacerbations will be derived similarly to primary endpoint in Section 3.2.1.1 and will be used for the production of summary statistics.

3.2.2.4 Time to first severe COPD exacerbation

A severe exacerbation event will be defined in the same way as outlined in Section 3.2.1.1.

Time from randomisation to first severe COPD exacerbation through Visit 16 (EOT) will be derived using the same approach as in Section 3.2.2.1. The time to first severe COPD exacerbation for subjects who complete Visit 16 (EOT) and do not experience a severe COPD exacerbation will be censored at Visit 16 date. For subjects lost to follow-up, prematurely withdrawing from the study, or discontinue the study treatment and remain in the study, the time to first severe COPD exacerbation will be censored at the end of the maximum follow-up time, as described in Section 3.2.1.1.

3.2.2.5 Change from baseline in pre-dose/pre-BD FEV₁ (L) at Week 52

Pre-dose/pre-BD FEV₁ (L) will be determined by spirometry at the clinic visit. The change in FEV₁ (L) from baseline to each of the post-randomisation visits (post Visit 3) up to and including the Week 52 visit (Visit 16) will be assessed with change from baseline at Week 52 used as the secondary efficacy variable.

Change from baseline is obtained as an absolute difference between Week 52 measure and the baseline value as defined in Section 3.1.2 and Section 3.1.3. Changes from baseline at other post-baseline time points will be calculated similarly.

3.2.2.6 St. George's Respiratory Questionnaire (SGRQ)

The change from baseline in SGRQ total score up to Week 52 will be another secondary endpoint.

The SGRQ is a 50-item PRO instrument developed to measure the health status of subjects with airway obstruction diseases ([Jones et al 1991](#)). The questionnaire is divided into two parts: part 1 consists of 8 items pertaining to the severity of respiratory symptoms in the preceding 4 weeks; part 2 consists of 42 items related to the daily activity and psychosocial impacts of the individual's respiratory condition. The SGRQ yields a total score and three component scores (symptoms, activity, and impacts). The total score indicates the impact of disease on overall health status. This total score is expressed as a percentage of overall impairment, in which 100 represents the worst possible health status and 0 indicates the best possible health status. Likewise, the component scores range from 0 to 100, with higher scores indicative of greater impairment. SGRQ will be completed using an electronic subject diary (eDiary) as specified in Table 2 of the CSP.

The symptoms component score will be set to missing if there are >2 missing items; activity component score will be set to missing if there are >4 missing items; impacts component score will be set to missing if there are >6 missing items; and total score will be set to missing if one of the 3 component scores is missing.

To avoid incorrectly setting component and/or total scores to missing when items are logically skipped, the following items should **not** be considered as missing if logically skipped in the context of the subject's prior responses:

Question 6 (Length of worst attack of chest trouble):

If no severe or very bad, unpleasant attacks of chest trouble are reported in Q5, the length of the worst attack (Q6) will be logically skipped and should be imputed as zero, with the weight for Q6 remaining in the denominator.

Question 8 (Wheeze worse in the morning):

If the frequency of wheezing attacks is reported as 'None' in Q4, Q8 ('Wheezing worse in the morning') will be logically skipped and should be imputed as zero, with the weight for Q8 remaining in the denominator.

Question 14 (Medication does not help very much, Embarrassed using medication in public, Having side effects from medication, Medication interferes with life a lot):

If a subject is not taking any relevant medication, Q14 will be logically skipped. Therefore, if **all 4** responses are missing, all should be imputed as zero and the denominator for the component / total score(s) unchanged.

Potential health status treatment benefits of tezepelumab will be evaluated by comparing the change from baseline at Week 52 in SGRQ total score. A 4-point threshold will be used to define the response. If SGRQ total score at Week 52 has a ≥ 4 -point decrease from baseline, it is defined as "improvement";

if it has a ≥ 4 -point increase, it is defined as “worsening”. If the SGRQ total score change at Week 52 is less than 4-points, it will be defined as “no change”. Missing SGRQ total score change at Week 52 will be considered as “not evaluable”. For the responder analysis of SGRQ, a responder will be defined as an individual who had “improvement” at Week 52 (i.e., ≥ 4 -point decrease in SGRQ total score at Week 52). Subjects who had SGRQ total score change defined as “no change” or “worsening” will be considered as non-responders. If SGRQ total score change at Week 52 is not evaluable due to missing data, then the subject will also be treated as non-responder.

3.2.2.7 Proportion of subjects achieving a decrease of ≥ 4 -points in SGRQ total score at Week 52 (MCID)

Based on empirical data and interviews with subjects, a decrease of ≥ 4 -points in SGRQ total score at Week 52 is associated with a MCID and all the subjects meeting this criterion (as a decrease from baseline) are classified as responders, as defined in Section 3.2.2.6. Specific details on the scoring algorithms are provided by the developer in a user manual ([Jones et al 2009](#)).

In the statistical analysis, a binary variable taking on the value 1 if a subject has experienced a MCID at Visit 16 (EOT) and 0 otherwise, will be used as the response variable.

3.2.2.8 COPD Assessment Test (CAT)

The CAT is an 8-item PRO developed to measure the impact of COPD on health status ([Jones et al 2009](#)). The instrument uses semantic differential six-point response scales, which are defined by contrasting adjectives to capture the impact of COPD. Content includes items related to cough, phlegm, chest tightness, breathlessness going up hills/stairs, activity limitation at home, confidence leaving home, sleep and energy. A CAT total score is the sum of item responses. Scores range from 0-40 with higher scores indicative of greater COPD impact on health status. A score cannot be calculated if > 2 responses are missing; when one or two items are missing, their scores can be set to the average of the non-missing item scores.

The CAT will be measured at visits in accordance to Table 1 and Table 2 of the CSP.

3.2.2.9 Additional supportive endpoints to secondary

To evaluate the effect of tezepelumab as compared to placebo on severe COPD exacerbations, proportion of subjects with ≥ 1 severe COPD exacerbations will be used as supportive variable to the secondary efficacy variable.

A severe exacerbation event will be defined in the same way as outlined in Section 3.2.1.1. In the statistical analysis, a binary variable taking on the value 1 if a subject has experienced one or more severe exacerbations during the 52-week double blind treatment period and 0 otherwise, will be used as response variable.

3.2.3 Exploratory endpoints

3.2.3.1 Composite Exacerbations (COPDCompEx) event

A composite endpoint for exacerbations (moderate or severe) in COPD (COPDCompEx) will be derived and analysed. COPDCompEx combines exacerbations with events defined from subject daily diaries. The definitions for both types of exacerbation are as follows:

- Exacerbations: episodes leading to one or more of the following: hospitalisation, emergency room visit, treatment with systematic corticosteroids, or treatment with antibiotics.
- Diary events: defined by meeting threshold and/or slope criteria for the following diary variables: breathlessness, cough, sputum, sleep, chest tightness, and rescue medication use. Breathlessness, cough, sputum, sleep, and chest tightness scores will be taken from the EXACT-PRO eDiary (recorded daily, in the evening) using variables EXACT07, EXACT02, EXACT03, EXACT13 and EXACT06 respectively, all of which are measured on a scale of 1-5. Rescue medication use will be calculated as described in Section 3.2.3.6 EXCEPT that daily use will be the sum of the morning and evening use **from the same day** (so that daily use is from evening to evening, to be consistent with the EXACT-PRO diary score recall period).

Threshold criteria:

- An increase of at least 2 puffs from baseline in rescue medication use (during 24h),
and
- An increase from baseline of at least 1 unit or maximum scores in all of the following symptom scores (during 24h): breathlessness, cough, sputum, sleep, and chest tightness.

Slope criteria:

- Need to meet the threshold criterion for at least one variable (either rescue medication use, breathlessness, cough, sputum, sleep or chest tightness) for two consecutive days (for the same symptom variable),
and
- Need to have the slope of a regression fit in the preceding 5 days to meet the following for all 6 variables:
 - Rescue medication slope ≥ 0.3 doses/day
 - Breathlessness slope ≥ 0.1 units/day
 - Cough slope ≥ 0.1 units/day
 - Sputum slope ≥ 0.1 units/day
 - Sleep slope ≥ 0.1 units/day

- Chest Tightness slope ≥ 0.1 units/day

In all of the above cases, the regression slope is the point estimate of the slope obtained from a linear regression of the values of each of the 6 variables separately against day number, with no other variables included in the regression model.

The following table shows how the timing for the 5-day requirement for the regression slopes fits with the 2 consecutive day requirement, where “Day 0” here refers to the first of the 2 consecutive days (shaded) to be used each time the rolling 2 consecutive day assessment is made:

Table 2 Timing for assessment of COPDCompEx slope criterion

	Day -4	Day -3	Day -2	Day -1	Day 0	Day 1
Threshold					x	x
Slope	x	x	x	x	x	

A regression slope will be calculated provided there are at least 2 non-missing values in the required 5 days. Day 0 must be at least 1 day after the treatment start date to be able to estimate the slope.

Baseline is determined as the average of each variable using the 14 last days of the run-in period for each subject.

The start date of a COPDCompEx event is defined as the earliest of the exacerbation or diary events start dates which meets the definition. Exacerbation start date is as stated in Section 3.2.1.1. Diary event start date is defined as the earliest Day 0 (in notation from above table) from any series of rolling 2 consecutive days which first qualifies using either the threshold or slope criterion.

The end date of a COPDCompEx event is defined as the latest of the exacerbation or diary events start dates which meets the definition. Exacerbation end date is as stated in Section 3.2.1.1. Diary event end date is defined as the latest Day 1 (in notation from above table) from any series of rolling 2 consecutive days which last qualifies using either the threshold or slope criterion.

Similarly to the primary endpoint, if the end date of the first COPDCompEx event and the start date of the second COPDCompEx event are less than 7 days apart for any subject, then these will be counted as one COPDCompEx event.

The analysis of this endpoint will primarily be time to first COPDCompEx event defined similarly to the secondary endpoint in Section 3.2.2.1, namely

Start date of first COPDCompEx event - Date of randomisation + 1

If a subject presents either an exacerbation as described above, or any diary event meeting the threshold and slope criteria, COPDCompEx will be 1 (otherwise it will be 0). For those subjects with COPDCompEx=1 the date when the event (either exacerbation, or diary events) occurred will be also recorded. Subjects with COPDCompEx=0 will be considered as censored in that period. The date of censoring will follow the same rules as for time to first COPD exacerbation in Section 3.2.2.1.

In addition, the annual COPDCompEx rate, defined similarly to the primary endpoint in Section 3.2.1.1, in the tezepelumab group will be compared to that seen in the placebo group using a negative binomial model. The maximum follow-up time will be up to Week 12 (Visit 6) and Week 52 (Visit 16) with the assessment of the last COPDCompEx event status widened to also include additional consideration of the last assessment of various eDiary events used in the COPDCompEx definition. For subjects who prematurely withdraw from the study prior to Week 12 (Visit 6) or Week 52, the follow up time will be up to the date of the last assessment available.

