8.1.4 COPDCompEx

COPDCompEx is a composite endpoint for exacerbations (moderate or severe) in COPD. COPDCompEx combines exacerbations with events defined from patient daily diaries. The definitions for both types of exacerbation are as follows:

- **Exacerbations:** episodes leading to one or more of the following: hospitalization, emergency room visit, treatment with systemic corticosteroids, or treatment with antibiotics.
- **Diary events**: defined by threshold and slope criteria using the following diary variables: individual domains of the breathlessness, cough, sputum scale, sleep, chest tightness and rescue medication use.

The analysis of this endpoint will primarily be time to first COPDCompEx event, but the events may also be analysed with models addressing event rates or time to recurrent event. More details on the derivation and analysis of this variable will be given in the Statistical Analysis Plan (SAP).

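### SAP 3.2.3.1 defines the exploratory COPDCompEx endpoint inconsistently: and versus or for diary events, an end date built from start dates, and a merge rule that differs from the primary endpoint's

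*SAP*

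**What the plan says.** COPDCompEx combines exacerbations with events derived from the daily diary. Protocol 8.1.4 describes the diary events as "defined by threshold and slope criteria using the following diary variables" and leaves the detailed derivation to the SAP.

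SAP 3.2.3.1 then gives:

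- a definition: "Diary events: defined by meeting threshold and/or slope criteria for the following diary variables";
- a diary-event start date, the earliest qualifying day "from any series of rolling 2 consecutive days which first qualifies using either the threshold or slope criterion", and a diary-event end date with the same either/or condition;
- an event indicator: "any diary event meeting the threshold and slope criteria, COPDCompEx will be 1 (otherwise it will be 0";
- a composite end date: "The end date of a COPDCompEx event is defined as the latest of the exacerbation or diary events start dates which meets the definition". The next two sentences define end dates for the exacerbation and for the diary event;
- a merging rule, introduced as similar to the primary endpoint's: two events that "are less than 7 days apart for any subject, then these will be counted as one COPDCompEx event".

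SAP 3.2.1.1, for the primary endpoint, merges exacerbations whose end and next start are 7 days apart or less, counts overlapping exacerbations as one, and subtracts event days plus the following 7 days to obtain time at risk. SAP 3.2.3.1 defines the COPDCompEx rate similarly to that section, and SAP 4.2.6 uses log time at risk as the offset. SAP Section 6 reports no change of analysis from the protocol.

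**The concern.** The and/or conflict decides who has an event. Under the either/or sentences, a subject who meets only one criterion has a dated diary event. Under the indicator sentence the same subject has COPDCompEx = 0 and is censored. That reaches the time-to-first-event analysis, which the SAP treats as the main one for this endpoint, and also the rates.

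The end-date sentence and the merging rule act elsewhere. They determine how long an event lasts, when a second event is counted, and how many days leave the offset. Two programmers following this section in good faith could produce different indicators, counts and times at risk. If the choice is left until results are visible, it can no longer be shown to be independent of them.

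**Working it through.** The documents state no sample size, event count or rate for COPDCompEx, so there is no plan figure to reproduce. The check is a comparison of the sentences, followed by worked dates.

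**1. And versus or**

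| Sentence | Rule |
|---|---|
| Protocol 8.1.4, diary events | and |
| SAP 3.2.3.1, definition of diary events | and/or |
| SAP 3.2.3.1, diary-event start date | either |
| SAP 3.2.3.1, diary-event end date | either |
| SAP 3.2.3.1, event indicator | and |

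Neither criterion implies the other. A subject whose six variables all sit on a raised plateau meets the threshold criterion, but the five-day slopes can be zero. A subject with all six slopes rising and only one variable above its threshold for two consecutive days meets the slope criterion but not the full threshold. Events under *and* are therefore a subset of events under *or*.

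An illustrative simulation shows that the difference can be large. Diary noise, episode frequency (2.5 per year) and three episode sizes were all assumed, with 800 subjects per setting, and *and* was taken to mean both criteria in the same two-day window. The share of subjects with a diary event by 12 weeks was 0.50, 0.55 and 0.51 under *or*, against 0.04, 0.20 and 0.35 under *and*. None of these figures comes from the documents.

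**2. End date**

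Days removed from follow-up = (end − start + 1) + 7, from SAP 3.2.1.1. Days are counted from the start of the event.

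Lone exacerbation, Days 0 to 14 (assumed example):

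- literal rule, end = Day 0: (0 − 0 + 1) + 7 = 8 days removed;
- end-based rule, end = Day 14: (14 − 0 + 1) + 7 = 22 days removed;
- overstatement of time at risk: 22 − 8 = 14 days.

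In an 84-day (12-week) window this is 84 − 8 = 76 against 84 − 22 = 62 days at risk, a factor of 76/62 = 1.23 for that subject. Over 364 days (52 weeks) it is 356 against 342, a factor of 1.04.

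Same exacerbation with a diary event that starts on Day 10 and ends by Day 14:

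- end-based: one event, 22 days removed;
- literal, components handled separately: the gap is 10 − 0 = 10 days, so two events; Days 0–7 and 10–17 are removed, 8 + 8 = 16 days; the error is 22 − 16 = 6 days plus one extra event;
- literal, components treated as one event ending on Day 10: (10 − 0 + 1) + 7 = 18 days removed, an error of 4 days;
- with the overlap rule of SAP 3.2.1.1 carried over: one event.

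**3. Merging**

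| Days from end to next start | Merge if < 7 (COPDCompEx) | Merge if ≤ 7 (primary) |
|---|---|---|
| 6 | 1 event | 1 event |
| 7 | 2 events | 1 event |
| 8 | 2 events | 2 events |

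At a gap of 7 days, the second event starts on the last of the 7 days that the time-at-risk rule has already removed. It is counted on a day when the subject is not at risk.

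**Reach.** Time to first event is the start date of the first event minus the randomisation date plus 1. End dates and merging do not enter it, so items 2 and 3 bear on the rate models only.

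**The case against.** The strongest reply is that this is an exploratory endpoint with nominal p-values and that the wording is recoverable.

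- The word *and* in the indicator sentence and the protocol may simply name the two sets of criteria. The slope criterion already asks for one variable to meet its threshold on two consecutive days, a clause that would be largely redundant if the full threshold were also required.
- The end-date sentence looks like a one-word slip, because the component end dates defined immediately after it have no other use.
- The overlap rule in SAP 3.2.1.1, if carried over, prevents an episode from being split.
- If *less than 7 days apart* counts clear days, the merging rule may equal the primary one, since dates 7 apart leave 6 clear days.

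Much of this stands, and it limits the weight of the point. It does not settle the text. The redundancy argument favours *or*, but Protocol 8.1.4 still reads *and*, and SAP Section 6 lists no change. The SAP does not say that the overlap rule takes precedence over the explicit end-date sentence. A probable slip in a derivation rule still needs correcting before it is programmed.

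**Conclusion.** The inconsistencies are in the text and no other section resolves them. The and/or conflict carries the most weight: it leaves the event indicator, the Cox analysis and the rates undetermined until reconciled. Applied literally, the end-date sentence gives wrong durations and offsets. The merging difference is marginal.

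A reader might infer three stronger conclusions that the documents do not support.

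- That all three items distort the Cox analysis: only the and/or rule does.
- That 14 days is the general error in time at risk: it belongs to a lone exacerbation on Days 0 to 14. The overlapping example gives 6 or 4 days, and splitting into two events depends on not applying the overlap rule.
- That *or* is plainly the intended rule: the SAP's internal logic leans that way, but the protocol's wording does not.

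The sizes rest on assumed dates and are per subject. Without event rates or durations for COPDCompEx in the documents, the effect on the rate ratios cannot be sized. The primary and secondary endpoints are unaffected.

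**What to change.** Before unblinding, amend SAP 3.2.3.1 as follows.

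1. State one rule, *and* or *or*, in all four sentences (definition, diary start date, diary end date, indicator) and reconcile it with Protocol 8.1.4. If *or* is kept, list it in SAP Section 6 as a change from the protocol. If *and* is chosen, say whether both criteria must be met in the same two-day window.
2. In the composite end-date sentence, replace start dates with end dates.
3. Merge events at 7 days or less, as in SAP 3.2.1.1, and state that the overlap rule of that section applies to COPDCompEx.

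The cost is SAP wording and a matching check of the derivation program. No new data or additional analyses are needed.

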3.2.3.2 Clinically Important Deterioration (CID) event

CID is a composite endpoint measuring worsening of the key clinical features of COPD, namely lung function, subject-reported outcomes, and exacerbations. CID is defined as having met at least one of the following criteria:

- ≥ 100 mL decrease in pre-dose/pre-BD FEV₁ (L) compared to baseline
- Decline in health-related quality of life defined as ≥ 4 unit increase from baseline in SGRQ total score
- Occurrence of a moderate or severe on-treatment COPD exacerbation

Time to CID event will be used as the outcome variable to explore the effect of tezepelumab and it is defined as follows:

Start date of CID event - Date of randomisation + 1

where the start date of the CID event will be the assessment date of any of the three conditions above, whichever occurs first.

Subjects will be evaluated for CID events up to Week 52. The time to CID event for subjects who complete Visit 16 (EOT) and do not experience a CID event will be censored at Visit 16. For subjects lost to follow-up, prematurely withdrawing from the study, or discontinue the study treatment and remain in the study, the time to CID event will be censored at the end of the maximum follow-up time, as described in Section 3.2.1.1.

